Alcohol use is inextricably linked to the HIV epidemic in fishing communities on Lake Victoria in Uganda, where HIV incidence among regular drinkers is 5 times higher than among non-drinkers.¹ Fishing communities are an HIV “hotspot;” HIV prevalence in fishing communities is estimated at >25%²⁻⁴ compared to the national prevalence of 7.3%.⁵ Prevalent alcohol consumption is also consistently reported across a range of studies with fisherfolk in Uganda^{3, 4, 6-8} and hazardous and harmful alcohol use, especially among *fisherfolk men*, is dramatically more prevalent (37%)⁶ than in the general population (5.8%).⁹ In our preliminary research Among the 61% of men who reported alcohol use, 60.2% had AUDIT scores (>7) indicative of hazardous/harmful alcohol use and 16% had AUDIT scores (>16) indicative of a high level of alcohol problems.⁶ Heavy alcohol use is especially problematic among individuals living with HIV as it leads to poor treatment outcomes¹⁰ and is associated with suboptimal antiretroviral (ART) adherence and engagement in care.¹¹⁻¹³

Like much of Uganda’s economy, fishing villages operate on a cash economy; workers get daily cash payments for their work but have limited mechanisms for savings due to a lack of access to traditional banking infrastructure. Poverty and stressful work conditions paired with easy access to alcohol and cash with no means of savings (i.e., access to banks, savings accounts) may be drivers of alcohol consumption among fisherfolk men.¹⁴ Moreover, frequent mobility and work responsibilities, a lack of social support, HIV stigma, and distance to the clinic have been shown to impede access to HIV care services among fisherfolk.^{15, 16} Given the unique context of heavy alcohol use and challenges with engaging fisherfolk men in HIV care, a combination intervention, which addresses structural as well as behavioral factors may be needed for this population.

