Research setting. The study will be conducted in Wakiso District, Uganda which is on the northern side of Lake Victoria. Our team has conducted several studies in fishing communities in this district. Majority of residents of fishing villages work in the fishing industry and individuals receive daily cash payments for their work. The study will take place at 5 HIV clinics in Wakiso District which serve large populations of fisherfolk. *Fisherfolk* include fishermen, fish traders, fish processors, fish loaders, boat/fishing equipment repairmen, and other workers who engage in work supporting the fishing industry within the fishing communities. As of May 2018, there were over 1,700 adult male patients on ART at these clinics.

Study population. The study population is fisherfolk men aged 18-50 who engage in heavy alcohol use. The age range focuses on men who are the most high risk group for HIV and unhealthy alcohol use.^{5, 9}

Inclusion criteria: men aged 18-50; work as a fisherman, fish trader, fish processor, fish loader, related occupation supporting the fishing industry; living with HIV; on antiretroviral treatment for at least 1 month, report missing 1 or more dose of ART in the prior 2 weeks; **Alcohol use criteria:** consumed 5 or more drinks per occasion 2 or more times in the prior month or have an AUDIT-C (Alcohol Use Disorder Identification Test-Concise) score of ≥ 4 ¹⁹; not planning to move from the area within the next 6 weeks; have their own mobile phone and can be reached via phone (nearly all ($>97\%$) fisherfolk men have their own mobile phones and receive incoming calls is free).

Consuming ≥ 5 drinks per occasion is the definition of heavy episodic drinking or binge drinking, as defined the National Institutes of Alcohol Abuse and Alcoholism (NIAAA). This type of drinking is the most concerning type of alcohol use for individuals who are HIV positive. Recent longitudinal data has shown that greater frequency of heavy alcohol use is directly associated with poor ART adherence and an important clinical outcome (lower CD4 count) and is indirectly associated with higher HIV viral load (via lower adherence).¹⁰ Based on this evidence, we focus on heavy alcohol use for this intervention, and restrict our sample to those reporting recent heavy/binge alcohol use.

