3.4 Measures

Unless otherwise noted all variables will be assessed at baseline and at follow-up, 3 and 6 months from baseline.

Primary alcohol outcome. We will use an **alcohol biomarker**: phosphatidylethanol (PEth) as the primary alcohol outcomes assessed at baseline and 6-month follow-up. PEth is a phospholipid which is formed only in the presence of alcohol and thus is highly specific.⁴⁷ PEth has shown good performance as a medium-term biomarker⁴⁸ and in controlled laboratory studies, correlated well with level of consumption (Spearman's $r = 0.6-0.8$).⁴⁹⁻⁵²

We will also use the AUDIT-C¹⁹ as another measure of hazardous alcohol use.

ART adherence: We will assess adherence to ART using the AIDS Clinical Trials Group Adherence measures (AACTG),⁵³ which includes recall questions about ARVs missed for the previous 4 days prior to the interview. It has demonstrated construct validity in Uganda and similar settings⁵⁴ and shows strong correlations with HIV VL⁵⁵ and moderate correlations with electronic adherence monitoring.⁵⁶

Measures and analysis for assessment of feasibility:

To inform a future larger randomized trial of the *KISOBOKA* intervention we follow Bowen et al.'s suggestions for conducting feasibility studies in preparation for larger RCTs²⁴ which includes assessing feasibility on the following dimensions: **acceptability, demand/use, implementation, and practicality**. We will document the number of intervention sessions participants attended which will speak to demand for/use of the intervention. To monitor implementation for the individual and group intervention sessions we will audio record intervention sessions and transcribe and code 20% of sessions to monitor intervention fidelity. Related to the practicality of the procedures, we will assess our retention rate through the 6-month follow-up to determine if we will need to develop additional retention procedures to maximize retention in a larger trial with a longer follow-up.

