Data security: Data directly entered from the questionnaire interviews will be automatically encrypted and then uploaded onto a secure server. Only the PIs and data manager will have access to the server. No participant names will be stored in the database. All participants will be identified by a unique identifier, a random number assigned to them at the time of recruitment. In the event of loss of data or theft, all data files will be encrypted, and no outside user would be able to access the data. To ensure that no data that is collected is lost, encrypted data will be backed up on several sources: a separate server and copied to a secondary encrypted database used by the PI and biostatistician for additional processing.

Statistical Analysis Plan

A key objective of this study is to explore the effectiveness of the intervention vs. control and obtain effect size estimates to be used to design a future trial of this intervention. The primary outcomes are PEth scores, AUDIT-C score, and ARV adherence. Different statistical methods will be utilized depending on the type of outcome variable and whether minimum conditions for use of the methods are met. For example, log Gamma models may be used to analyze the difference in PEth scores between intervention and control groups given the expected distribution of PEth scores. An intent to treat approach will be utilized to determine analytic sample. Variables (except PEth which is measured at 2) will be measured at three time points (baseline, 3 and 6 months) so the dependency from the repeated measures must be considered. Information criterion such as AIC and BIC will be used to select the most appropriate covariance structure to address dependence. Generalized estimating equations (GEE) will be built to examine the intervention effect on our outcomes of interest across time points (baseline, 3 and 6 months), adjusting for repeated measurement, using a time*condition interaction term. Potential covariates for each adjusted model will be identified a priori from the literature and added to the model. Correlation matrices will be determined based on model fit. Statistically significant covariates will be retained in final fitted models using an alpha of 0.05.

4 Ethical considerations

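### The GEE takes the effect from an unconstrained time-by-condition interaction with baseline as a response, which costs some precision that a common baseline mean or baseline adjustment would recover

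*Combined protocol and SAP*

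**What the plan says.** The Statistical Analysis Plan in section 3.5 uses GEE models to "examine the intervention effect on our outcomes of interest across time points (baseline, 3 and 6 months"). The same sentence describes these models as "adjusting for repeated measurement, using a time*condition interaction term". Baseline is therefore a response time point. For PEth, which has only baseline and 6-month values, "log Gamma models may be used to analyze the difference in PEth scores between intervention and control groups"; section 3.4 names "phosphatidylethanol (PEth) as the primary alcohol outcomes assessed at baseline and 6-month follow-up". On the working correlation the plan says: "Correlation matrices will be determined based on model fit".

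Three things are not stated: whether the arms share one baseline mean, whether the baseline outcome is a covariate, and which contrast is the reported effect (6 months, both follow-ups, or a slope). The list of potential covariates in section 3.2 contains no baseline outcome.

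The sample size paragraph in section 3.2 gives 80 men per arm and 25% attrition, and says the pilot's purpose is effect-size estimates for a later trial rather than a powered test.

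**The concern.** Randomisation makes the true baseline means of the two arms equal. A model with condition, time and their interaction does not use this: it estimates a separate baseline mean per arm and subtracts it in full. With visit as a factor and an identity link, the 6-month interaction is the difference between arms in mean change. In large samples that is never more precise than a baseline-adjusted comparison, or than a common-baseline-mean model with a well-fitting working covariance.

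At stake is the width of the intervals around the estimates the pilot exists to supply, from about 120 men with 6-month data (160 × 0.75). The baseline values are collected anyway.

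**Working it through.** **The plan's own figures.** None concerns precision. The stated powers (72% and 85% at d = 0.2) cannot supply the baseline-to-follow-up correlation r. Read as a single contrast with 60 per arm at an assumed two-sided 5% level, they imply r of about 0.91 and 0.93; a repeated-measures ANOVA reading of the 85% implies about 0.67. So r is assumed, over 0.4–0.7.

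**Other inputs.**
- From section 3.2: 80 per arm, 25% missing at 6 months. Assumed: 12.5% missing at 3 months, monotone.
- Selection (section 3.1): men "consumed 5 or more drinks per occasion 2 or more times in the prior month or have an AUDIT-C" score of at least 4. The resulting baseline SD is not given. As a proxy, the introductory background says of drinkers that "60.2% had AUDIT scores (>7) indicative of hazardous/harmful alcohol use". That leaves 1 − 0.602 = 39.8% of drinkers, or 1 − 0.61 × 0.602 = 63.3% of all men, below that level. Cuts of 0% and 20% are added because the entry rule has two alternative routes.
- Assumed: normal scores, unit SD and equal correlations before selection, exchangeable working correlation.

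**Step 1: two visits, closed form.** Let v be the baseline variance after selection. The slope of follow-up on baseline stays r and the residual variance 1 − r². Per arm of n men:
- baseline-adjusted: (1 − r²)/(0.75n)
- unconstrained change: (1 − r²)/(0.75n) + (1 − r)²v/n
- ratio: 1 + 0.75v(1 − r)/(1 + r)

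At r = 0.5 and v = 1 the ratio is 1 + 0.75 × 0.5/1.5 = 1.25, so the SE falls by 1 − 1/√1.25 = 10.6%.

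**Step 2: v after a lower cut at quantile q.** v = 1 + aλ − λ², with a = Φ⁻¹(q) and λ = φ(a)/(1 − q). This gives v = 0.583, 0.424 and 0.296 at q = 20%, 39.8% and 63.3%. With v = 0.424 and r = 0.5 the ratio is 1.106 and the SE falls by 4.9%.

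**Step 3: AUDIT-C, three visits.** Large-sample sandwich variance A⁻¹BA⁻¹, where A sums X′W⁻¹X and B sums X′W⁻¹SW⁻¹X over men. In S: Var(Y0) = v, Cov(Y0,Yt) = rv, Var(Yt) = 1 − r²(1 − v), Cov(Y3,Y6) = r − r²(1 − v). Fall in the 6-month SE from forcing in baseline:

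| Cut | r = 0.4 | 0.5 | 0.6 | 0.7 |
|---|---|---|---|---|
| none | 13.1% | 10.7% | 8.4% | 6.2% |
| 20% | 8.3% | 6.7% | 5.2% | 3.8% |
| 39.8% | 6.3% | 5.1% | 4.0% | 2.9% |
| 63.3% | 4.6% | 3.7% | 2.9% | 2.2% |

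At the 39.8% cut and r = 0.5 the variances are 0.02731 and 0.02460, and the 6-month SD after selection is √(1 − 0.25 × 0.576) = 0.925. The 95% half-width goes from 1.96√0.02731/0.925 = 0.350 SD to 1.96√0.02460/0.925 = 0.332 SD. That is worth 120 × (0.02731/0.02460 − 1) = 13 more men with 6-month data.

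A common baseline mean gives the same savings when the working covariance matches S. With an exchangeable one and a narrowed baseline it gives slightly less: in the same formula, 2.1% instead of 2.9% at the 39.8% cut and r = 0.7, and 1.0% instead of 2.2% at the 63.3% cut.

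**Step 4: PEth.** Simulated log Gamma GEE, two visits, 25% missing at 6 months, selection through consumption (correlation with log PEth 0.6–0.8, the range section 3.4 gives for PEth against consumption). A common baseline mean saves about 2–11% of the SE if PEth is gamma (CV 1) and 5–13% if lognormal (log SD 1). A second simulation at the 39.8% cut gave 9% and 3% (gamma) and 11% and 7% (lognormal) at r = 0.4 and 0.7. Monte Carlo error is about 1 percentage point. Forcing in log baseline PEth is less dependable: 16–24% if lognormal, but −2 to 11% if gamma.

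**Step 5: working correlation.** For AUDIT-C at the 39.8% cut, a common baseline mean fitted under independence has 0.96, 1.04, 1.17 and 1.36 times the variance of the unconstrained exchangeable contrast at r = 0.4, 0.5, 0.6 and 0.7. Under independence the gain can become a loss.

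**The case against.** The plan is a recognised, valid analysis. It does say how baseline is used: as a response. With baseline as a response one would not normally list it as a covariate too, so its absence from the covariate list is weak evidence of an omission. The study is declared not powered for differences, and at d = 0.2 an interval of ±0.350 or ±0.332 SD covers zero either way. All of this stands, and it keeps the point small.

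The size is also soft. The cuts come from the full AUDIT in a community survey, not from this trial's rule in clinic patients. Screening precedes the baseline questionnaire, and the documents do not say that one AUDIT-C score serves both. The PEth shapes and the exchangeable structure are assumptions, and log Gamma is itself only tentative in the plan. Hence ranges and no single figure.

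Stronger readings are tempting, but the documents do not support them:
- *That the SAP is silent on baseline.* It is not; what is missing is narrower.
- *That the interaction estimate is biased.* It is not.
- *That 15–25% of precision is lost.* That is (1 − r)/2 at r = 0.7 and 0.5, in variance units, with complete data and equal SDs. Attrition lowers it to about 12–20%, and selection on drinking lowers it further.
- *That the loss is only a few percent.* That needs a high r or a baseline clearly narrowed by eligibility, and the documents establish neither.

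**Conclusion.** The point holds as a low-severity improvement. The unconstrained reading gives up precision in the 6-month effect. For AUDIT-C the recoverable part is about 6–13% of the SE with no narrowing of baseline and about 2–8% with a 20–63% lower cut. For PEth it is roughly 2–13% with a common baseline mean. These figures rest on assumed r = 0.4–0.7, the assumed 3-month attrition, an exchangeable working correlation, and normal (AUDIT-C) or gamma or lognormal (PEth) shapes. No figure is claimed for ART adherence. No decision in the plan turns on the difference; the reason to act is that precise effect sizes are the pilot's purpose.

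**What to change.** In section 3.5:
- Name the 6-month difference between arms as the reported effect.
- AUDIT-C: either model the 3- and 6-month values on arm, visit and arm-by-visit with baseline AUDIT-C forced in, or keep all three visits and omit the condition main effect so that the arms share a baseline mean. The second keeps men with no follow-up in the model, which sits better with the intent-to-treat sample. The first drops them, and needs simple imputation for any missing baseline.
- PEth: keep both visits with time and time-by-condition but no condition main effect. This avoids taking the log of a zero baseline.
- Wherever a common baseline mean is used, pre-specify a non-independence working correlation instead of choosing it by fit.

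The cost is SAP wording; no new data are needed. With strong selection and high r the gain may be only about 2%, or about 1% for a common baseline mean under an exchangeable structure.

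### The SAP leaves open how covariates enter the GEE; entered as baseline main effects, they would add almost no precision to the AUDIT-C time-by-condition effect

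*Combined protocol and SAP*

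**What the plan says.** In the Statistical Analysis Plan (section 3.5), GEE models estimate the effect "across time points (baseline, 3 and 6 months), adjusting for repeated measurement, using a time*condition interaction term". Baseline is therefore one of the modelled responses, and the effect is a between-arm difference in change from baseline. No other interaction is named.

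On covariates the SAP has two sentences: "Potential covariates for each adjusted model will be identified a priori from the literature and added to the model", and "Statistically significant covariates will be retained in final fitted models using an alpha of 0.05". It does not say whether they enter as main effects or with visit interactions, or whether baseline or time-updated values are used. Section 3.4 makes both available: "Unless otherwise noted all variables will be assessed at baseline and at follow-up, 3 and 6 months from baseline".

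The model for AUDIT-C is also open: "Different statistical methods will be utilized depending on the type of outcome variable and whether minimum conditions for use of the methods are met". So is the working correlation: "Correlation matrices will be determined based on model fit". AUDIT-C is listed as a primary outcome under Study variables and again in the SAP. The sample size section anticipates 25% attrition.

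**The concern.** The plain reading is that covariates go in as main effects, because time by condition is the only interaction mentioned. A baseline covariate entered that way moves all of a man's fitted values by the same amount. The effect is a difference in change, so on an identity link the covariate has little to act on. The 0.05 retention rule does not help: applied to main effects, it selects covariates related to the level of AUDIT-C, not to its change.

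Three things are at stake:
- Precision that good covariates could supply is left unused.
- Chance imbalance in a covariate that predicts change stays uncorrected.
- An adjusted AUDIT-C estimate that nearly equals the unadjusted one by construction could be taken as support for it.

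The SAP makes effect-size estimates for a future trial a key objective, so the form of the adjusted model matters even in a pilot. If time-updated values were used instead, the problem would be a different one. Social support, motivation for care, delay discounting and income are all on the covariate list, and the intervention could plausibly change them.

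**Working it through.** The plan gives no figure for what adjustment contributes, so there is none to reproduce. Its power percentages do not bear on this point.

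**Inputs.** From the documents: 160 men at 1:1, visits at baseline, 3 and 6 months, baseline as a response, 25% attrition. Assumed, because not stated: identity link for AUDIT-C, visit as categorical, and all SDs, correlations and covariate strengths in the simulations.

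**1. Complete data.** Write E(Y_it) = a_t + b·G_i + d_t·G_i + c·X_i, with d_0 = 0, G the arm and X a baseline covariate. Then E(Y_i6 - Y_i0) = (a_6 - a_0) + d_6·G_i, and c·X_i has gone. The estimating equations set each arm-by-visit mean equal to the fitted value plus c times the arm mean of X. So the estimate of d_6 is the difference between arms in observed mean change, whatever c is.

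Simulated check (estimate / robust SE, a separate dataset for each working correlation):
- independence: -0.692095 / 0.366547 with and without covariates
- exchangeable: -0.355352 / 0.341504 with and without
- unstructured: -0.053521 / 0.343581 with and without

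**2. 25% random dropout.** Mean SE, exchangeable correlation:

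| Set-up | Unadjusted | Main effects | Covariate by visit |
|---|---|---|---|
| Four covariates, two predicting change | 0.1698 | 0.1665 | 0.1557 |
| Same, none predicting change | 0.1569 | 0.1560 | 0.1559 |
| Second set-up, covariates predict change | 0.403 | 0.396 | 0.370 |
| Third set-up, three covariates | 0.372 | 0.369 | not run |

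In the first row, main effects give 0.1665/0.1698 = 0.981, or 2% smaller. Visit interactions give a further 0.1557/0.1665 = 0.935, or 6.5% smaller. In the third row the ratios are 0.396/0.403 = 0.983 and 0.370/0.396 = 0.934. In the fourth, 0.369/0.372 = 0.992. A further set of runs put the gain from visit interactions at the lower end of 3 to 7%.

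In the fourth set-up the estimate moved by 0.039 on average. Under independence it moved by 0.097, and the SE went from 0.392 to 0.375 (4% smaller).

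**3. Dropout that depends on the covariate differently by arm** (true effect -0.5, mean estimates):

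| Covariate predicts | Unadjusted | Main effects | Covariate by visit |
|---|---|---|---|
| Level only, exchangeable | -0.631 | -0.499 | not run |
| Level only, independence | -0.889 | -0.534 | not run |
| Level and change, set-up A | -0.846 | -0.669 | -0.479 |
| Level and change, set-up B | -0.481 | -0.315 | -0.479 |

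In set-up A the bias goes from 0.346 to 0.169, so main effects leave about half. In set-up B the level part (-0.481 + 0.315 = -0.166) had been offsetting the change part (-0.315 + 0.5 = +0.185). Main effects removed only the first.

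**4. Other links.** On complete data with a log link, the interaction is unchanged under Poisson variance (-0.1208) but moves under Gamma variance (-0.1208 to -0.1334). In a log-Gamma PEth model, main effects lowered the SE from 0.223 to 0.200. On a logit link, adjusted and unadjusted estimates correlated at 0.99 to 1.00, and adjustment mainly rescaled the estimate.

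**5. Time-updated covariate affected by arm.** In one simulated dataset, adding it moved the effect from -0.991 to -1.229.

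**6. Baseline AUDIT-C as a covariate.** The variance ratio against a change score is (1 - r²)/[2(1 - r)] = (1 + r)/2. That is 0.65, 0.75 and 0.85 for r = 0.3, 0.5 and 0.7 (r is not given in the documents). In simulation with 25% random dropout and a common baseline slope, the SD of the 6-month effect was:
- 0.383 with baseline as a response
- 0.344 with baseline as a covariate (0.344/0.383 = 0.898)
- 0.331 with three covariates added (0.331/0.383 = 0.864)

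**The case against.** A reader might infer that the adjusted AUDIT-C model adjusts nothing and must return the unadjusted number. The documents do not support that, for three reasons:
- The plan expects 25% attrition. Covariates then move the estimate, and in step 3 main effects removed most or all of the bias when the covariate predicted level only.
- The SAP does not say that covariates are baseline values or main effects. Many of those listed can vary over time, and section 3.4 provides for repeated measurement.
- The AUDIT-C link is not stated, and the cancellation does not hold for every link and variance.

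Nor does any passage say that an adjusted result would be offered as confirmation of an unadjusted one. The argument also does not extend to PEth under the log-Gamma model that the SAP mentions, and section 3.4 names PEth as the primary alcohol outcome. Finally, the pilot is stated not to be powered, the precision gain is small, and nothing in the documents shows that any listed covariate predicts change.

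All of this stands as a limit on the point, but it does not remove it. Of the two open readings, one is nearly inert for precision and corrects bias only in part when the covariate predicts change. The other conditions on post-randomisation values. The SAP should say which it intends.

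**Conclusion.** The point holds as a gap in specification with a cheap improvement attached. With an identity link, categorical visits and complete data, the cancellation is exact and does not depend on simulation inputs. Under random dropout with an exchangeable correlation it is nearly so.

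Main effects do matter when dropout is related to a covariate differently by arm, and they are then incomplete if that covariate also predicts change. The sizes of the SE gains and of the bias rest on assumed variances, correlations and covariate strengths, so they show direction and order of magnitude only.

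An adjusted AUDIT-C estimate from main effects alone should not be read as independent confirmation of the unadjusted one. Severity is low: nothing here invalidates the primary analysis.

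**What to change.** In section 3.5:
- State the link for AUDIT-C.
- For AUDIT-C and any other identity-link outcome, name three or four covariates in advance, use their baseline values only, and enter each with its visit interaction.
- Replace the 0.05 retention rule with retention regardless of p-value.
- Preferably also move baseline AUDIT-C to the covariate side with its own visit interaction, and read the effect as the arm difference at 3 and 6 months.

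**Cost.** With baseline kept as a response, each covariate adds two parameters beyond its main effect, so four covariates add eight. With baseline moved across, only two response visits remain and each covariate adds one. There is no gain from the covariate-by-visit terms if the covariates do not predict change. Moving baseline across also means that men with no follow-up visit contribute no response, so the intent-to-treat wording should say how they are handled.
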